9.2.5 Study Completion

The percent of participants who complete the study, losses to follow-up, time to lost to follow-up, and reasons for discontinuation (e.g., adverse events) will be tracked and presented in tabular form. For the primary outcome (Tolerance as defined above), the analysis will be performed as per protocol for all participants who complete the modified rush visit. For immune / mechanistic outcomes, missing or spurious data will be excluded from analyses.

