Exclusion Criteria	 History of severe anaphylaxis Severe or Moderate asthma Poorly controlled asthma Diagnosis of other severe or complicating medical problems, including autoimmune or chronic immune inflammatory conditions or gastrointestinal inflammatory conditions Inability to cooperate with and/or perform oral food challenge procedures Primary Immune Deficiency Allergy to oat confirmed by skin prick testing and history Current use of beta blockers, angiotensin converting enzyme inhibitors, or monoamine oxidase inhibitors Women of childbearing potential who are pregnant, planning to become pregnant, or breastfeeding Use within the past 6 months of other systemic immunomodulatory treatments Hematocrit <0.36 for adult females or <0.38 for adult males Weight <23 kg
Investigational Product / Intervention	Active peanut flour vs. placebo oat flour
Study Procedures	OIT, DBPCFCs, physical examination, pregnancy testing, phlebotomy, PFTs
Statistical Considerations	n=40, 3:1 active to placebo; Per protocol analysis of the Treg proportion by clinical outcome for the anticipated 22 subjects completing DBPCFC3; effect size of 1.5 for primary outcome [?]; 27% (n=8) combined Partial Tolerance / Tolerance versus Treatment Failure (n=14).

Contents

1	BAC	CKGROUND AND RATIONALE	12
	1.1	Background	12
	1.2	Rationale for Selection of Study Population	12
	1.3	Investigational Product(s) / Intervention(s)	12
	1.4	Rationale for Selection of Investigational Product(s) / Intervention(s) and Regimen	13
	1.5	Preclinical and Clinical Experience	13
		1.5.1 Preclinical Studies	13
		1.5.2 Clinical Studies	14
	1.6	Risks	14
		1.6.1 Risks of Investigational Product(s) / Intervention(s)	14
		1.6.2 Risk of Study Procedures	14
		1.6.2.1 Double-blind placebo controlled food challenge (DBPCFC)	14
		1.6.2.2 Desensitization Procedure	15
		1.6.2.3 Allergy Prick Skin Testing	15
		1.6.2.4 Blood Draw	15
		1.6.3 Risk of Concomitant Medications, Prophylactic Medications and Rescue Medications	15
	1.7	Benefits	16
	• • •	1.7.1 Benefits of Investigational Product(s) / Intervention(s)	16
		1.7.2 Benefits of Study Procedure(s)	16
		1.7.2 Deficites of Study Frocedure(s)	10
2	OBJ	IECTIVES	16
	2.1	Primary Objective(s)	16
	2.2	Secondary Objective(s)	16
		2.2.1 Clinical:	16
		2.2.2 Mechanistic:	17
		2.2.3 Exploratory:	17
			• •
3	STU	DY DESIGN	17
	3.1	Study Endpoints	18
		3.1.1 Primary Endpoint(s)	18
		3.1.2 Secondary Endpoint(s)	18
	3.2	Study Completion	19
4	SEL	ECTION AND WITHDRAWAL OF PARTICIPANTS	19

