7 STUDY VISITS AND PROCEDURES

Appendix 16.1 summarizes the schedule of events for the study.

7.1 Enrollment and Randomization

Participants will be recruited from oral immunotherapy-interested individuals who have contacted us in response to announcements and advertisements, referrals from Allergy/ Immunology Clinics, and by identification using the Partners Research Participant Data Registry. The referring physician may send potential participants and/or their

23 of 68

parents a recruitment letter. The letter will include contact information for study staff so the participant and/or their parents can opt-in to participate. This research study will be explained in lay terms to each potential research participant. The potential participant or participant's legal guardian will sign an informed consent form before undergoing any baseline study procedures. Participants age 14-17 will co-sign the consent form with their legal guardian. Participants age 7-13 will sign a child-specific assent form and their legal guardian will sign the consent form.

Participants enrolled as minors will be provided an adult consent form for signature when they reach age 18 and will be re-consented before any study procedures take place. Any "new adult" who refuses consent will be removed from the study. Participants who are deemed eligible for the study (see section 4) will be enrolled and assigned a unique participant number.

Following DBPCFC1, participants will be randomly assigned by the study statistician to treatment or placebo groups at a ratio of 3:1. Following DBPCFC2, assignment will be unblinded and placebo participants will be offered open-label active treatment following the same desensitization procedures (Modified Rush, Build Up and Maintenance).

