9 SAMPLE SIZE CALCULATIONS AND STATISTICAL PLAN

9.1 Sample Size and Power Calculations

As the hypothesis regarding Treg induction and clonal tolerance can only be defined among those individuals who achieve desensitization and go on to DBPCFC3, the analysis will be per protocol for those participants who complete both post treatment challenges. The difference in the proportion of Treg will be compared between the groups using Students t test for comparison of means. Because we are expecting the primary outcome variable (difference in the proportion of Treg) to be log-normally distributed, we plan to carry out the t test on the log transformed variable. We will be powered at the expected effect on Treg if as few as six individuals (20% clinical effect and 10% dropout) who complete the protocol achieve our defined measure of at least partial clinical tolerance. Table 15.6 shows power calculations around these assumptions using a two sided t test at an alpha level of 0.05.

The sample size selected is 30 active treatment and 10 placebo treatment. We are applying the following assumptions for our power analysis (see Figure 15.5 for schema of assumptions).

- Approximately 27% of the Active Treatment group (8/30) will achieve Partial Tolerance (ED at DBPCFC3 <4430 mg but ≥430 mg AND >10-fold more than at DBPCFC1) or Full Tolerance (no reaction at DBPCFC3).
- The comparison of interest is between the combined Tolerance/Partial Tolerance and Active Treatment Failure groups who complete DBPCFC3.
- Those who fail to become desensitized after active treatment and those who receive placebo treatment are not fully informative for the primary endpoint and are therefore excluded for the per protocol analysis.
- The difference from baseline to the end of maintenance therapy in the mean proportion of induced Treg (CD45RA- CD25++ FoxP3++ of CD4+ T cells) between the Tolerance/Partial Tolerance and Treatment Failure groups will be 1.5 times the standard deviation.

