The placebo group will be used primarily to assess whether and to what extent there are more AEs associated with treatment. However, we will be able to also perform an intention to treat analysis of the primary outcome (difference in Treg proportion at the second blood draw from baseline) including the Placebo group. There is no expected effect on Treg in the placebo group and as above the comparison of interest is of outcomes within the actively treated participants who complete DBPCFC3. Estimating that 27% of active arm treatment achieve significant tolerance (n=8; see Figure 15.5) and that all Placebo group participants are defined as Treatment Failures after DBPCFC2 (n=10) and that the remaining Active Treatment participants will lose tolerance during avoidance (n=14), then we will have 100% power at an α level of 0.05 to detect the expected 1.5 X SD difference.

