9.2.2 Study Participant Populations

As described above, the per protocol sample will consist of all active treatment participants completing DBPCFC3.

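### Section 9.2.5 names Tolerance as the primary outcome and applies per protocol to everyone completing the modified rush, against the Treg primary endpoint and the active DBPCFC3-completer set defined elsewhere; separately, the 100% power in 9.1 should be about 0.945

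*Combined protocol and SAP*

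**What the plan says.** The synopsis, 3.1.1 and 9.2.4.1 all give the primary endpoint as the change in induced Treg proportion from baseline to the end of maintenance. Section 9.1 uses the term primary outcome in the same sense when it describes an "intention to treat analysis of the primary outcome (difference in Treg proportion at the second blood draw from baseline").

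The analysis set is also stated more than once. The synopsis has "Per protocol analysis of the Treg proportion by clinical outcome for the anticipated 22 subjects completing DBPCFC3", and 9.2.2 says that "the per protocol sample will consist of all active treatment participants completing DBPCFC3". Section 9.1 adds an exclusion: "Those who fail to become desensitized after active treatment and those who receive placebo treatment are not fully informative" for the primary endpoint, so both groups are left out of the per-protocol analysis.

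Section 9.2.5 then says: "For the primary outcome (Tolerance as defined above), the analysis will be performed as per protocol for all participants who complete the modified rush" visit. Its next sentence is "For immune / mechanistic outcomes, missing or spurious data will be excluded from analyses".

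For the intention-to-treat analysis, 9.1 counts 8 participants with significant tolerance, 10 placebo participants classed as failures after DBPCFC2, and 14 active participants who fail after avoidance. It concludes, for a 1.5 SD difference at α 0.05, "then we will have 100% power".

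**The concern.** Within section 9, primary outcome and per protocol each have two meanings. In one, the outcome is a continuous Treg change compared between two groups of active participants who reached Day 518. In the other, it is a clinical category assessed in everyone, in either arm, who got through a visit at Day 42. The plan gives a test and power for the first only.

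The trial has 40 participants and one powered comparison, so the primary variable and its analysis set should be fixed before anyone sees data. As the text stands, an analyst could follow 9.2.5 and report an unpowered analysis as primary, or could choose between the two after the results are known and cite the plan for either choice.

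The 100% power figure is a separate misstatement in the same section. It makes the intention-to-treat analysis look certain to detect the hypothesised effect.

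**Working it through.** **1. The two definitions side by side**

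| | 3.1.1, 9.1, 9.2.2, 9.2.4.1, Table 15.6 | 9.2.5 |
|---|---|---|
| Primary variable | Change in induced Treg proportion | Tolerance |
| Set called per protocol | Active participants completing DBPCFC3 (Day 518) | All completing the modified rush (Day 42) |
| Placebo | Excluded | Included |
| Size | 22 expected; 19 with dropout | Up to 40 |
| Test and power | t test on the log-transformed variable; Table 15.6 | None stated |

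**2. Size of the population difference**

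Section 9.1 plans 30 active and 10 placebo participants. The synopsis expects 22 active participants to complete DBPCFC3.

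- Active participants outside the 9.2.2 set: 30 − 22 = 8.
- Adding placebo: 8 + 10 = 18.
- Upper limit of the 9.2.5 set, if all complete the modified rush: 22 + 18 = 40.

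**3. Reproducing the plan's own power**

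Inputs from 9.1 and Table 15.6: two-sided t test, α = 0.05, difference d = 1.5 SD. With group sizes n₁ and n₂, df = n₁ + n₂ − 2 and the noncentrality is δ = d·√(n₁n₂/(n₁+n₂)). Power is the probability that a noncentral t variable with these values falls beyond the two-sided 5% critical value.

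- 8 v 14: δ = 1.5·√(112/22) = 3.38, df 20, power 0.896 (plan 0.90).
- 7 v 12: δ = 1.5·√(84/19) = 3.15, df 17, power 0.844 (plan 0.84).
- 6 v 13: δ = 1.5·√(78/19) = 3.04, df 17, power 0.817 (plan 0.82).

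All 18 cells of Table 15.6 reproduce within 0.01, so this is the plan's method.

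**4. The 100% figure**

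The 9.1 count is 8 against 10 + 14 = 24, so 8 + 24 = 32 participants. That leaves 40 − 32 = 8 randomised participants uncounted.

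- 8 v 24: δ = 1.5·√(192/32) = 3.67, df 30, power 0.945.
- 8 v 32, with the other 8 added as failures having the same mean Treg change: δ = 1.5·√(256/40) = 3.79, df 38, power 0.959.
- Other conventions for 8 v 24: normal approximation 0.957; one-sided t test 0.974. Neither rounds to 100%.
- With 8 v 24, power reaches 0.995, and so rounds to 100%, only from about 1.91 SD.

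**The case against.** The best defence is that 9.2.5 is loosely labelled and not a rival plan. It sits under Study Completion and gives no test or α for Tolerance. The endpoint sections, the stated t test and Table 15.6 all point to Treg, so the chance that the wrong variable is actually analysed as primary is small. The modified rush is also a sensible anchor for a clinical outcome, since 8.1.5 uses it as the point after which participants are not replaced. This stands as far as it goes: the population is coherent for clinical tolerance and should be kept. It does not remove the conflict over the words primary and per protocol. Reading Tolerance as only the grouping variable would soften the clash over the outcome but leave the clash over the population.

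A reader might infer more than the documents support:

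- **That Tolerance cannot be classified on placebo.** Section 7.1 says "Following DBPCFC2, assignment will be unblinded and placebo participants will be offered open-label active treatment", and Tolerance is defined at DBPCFC3. But Treatment Failure can be assigned without DBPCFC3, from not reaching 600 mg or from an ED below 1443 mg at DBPCFC2. Section 9.1 expects every placebo participant to be classed as a failure after DBPCFC2. Missing the third challenge because of open-label treatment leaves unclassified only a placebo participant with an ED of at least 1443 mg at DBPCFC2 who then takes that treatment.
- **That the sentence on immune and mechanistic outcomes removes Treg from the primary outcome.** It is a missing-data rule. An outcome can be both mechanistic and primary.
- **That objective 2.1 conflicts with the analysis because it names the whole Treatment Failure Group.** Section 9.1 settles this by stating both the comparison of interest and the exclusion.

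**Conclusion.** The contradiction is real on both counts. Section 9.2.5 differs from the rest of the plan in the primary variable and in who is in the per-protocol set: up to 40 people against about 22. It is a defect of definition. Table 15.6 is correct for the Treg comparison, and aligning the text changes none of its entries. A reader might take the conflict to mean that the trial is underpowered for its stated primary comparison. The recomputed 0.896, or 0.844 with dropout, does not support that.

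A smaller gap lies beside it. Section 9.1 excludes active participants who were not desensitised, while 9.2.2 asks only for completion of DBPCFC3. Section 5.6.1 calls active participants who react below 1443 mg at DBPCFC2 treatment failures but does not expressly bar them from DBPCFC3. The two sets could therefore differ.

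The 100% power claim is wrong for the counted groups: about 0.945, or about 0.96 if all 40 are included. It concerns an additional analysis and adds no weight to the 9.2.5 point. These figures rest on the plan's 1.5 SD, equal variances and the expected group counts; 8 v 32 also assumes that the extra 8 share the failures' mean.

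This should be fixed before analysis, and the remedy is small.

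**What to change.** 1. Amend 9.2.5 so that the primary outcome is the change in induced Treg proportion from baseline to the end of maintenance, analysed in the per-protocol set of 9.1 and 9.2.2. Add to 9.2.2 the exclusion in 9.1 of participants not desensitised at DBPCFC2, so that the two sections describe one set.
2. Keep modified-rush completers as the population for the clinical tolerance classification, labelled neither primary nor per protocol. It is the only population the plan states for that purpose and should not be lost. Say that anyone who meets a Treatment Failure criterion before or at DBPCFC2 is classed as a failure, as the existing definition allows.
3. In 9.1, replace 100% with about 0.945 for 8 v 24, and note that this covers 32 of 40 participants. If all 40 are meant, give about 0.96 for 8 v 32 and state the assumption.
4. Where the primary result is put into words, describe it as tolerance or partial tolerance versus failure at DBPCFC3 among desensitised active participants. Avoid keeping versus losing tolerance: 15.5 defines tolerance only at DBPCFC3, so those who fail there were never shown to be tolerant.

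The cost is wording in 9.1, 9.2.2 and 9.2.5 and one slightly less favourable figure, made through the amendment route in 9.4. No visits, samples or analyses are added, and Table 15.6 stays as it is.

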9.3 Interim Analyses

An interim safety analysis will be performed after the first five patients have undergone desensitization and dosage escalation. [name] has agreed to serve as an independent medical monitor during this analysis and also thereafter. The interim analyses will asses if the rate of adverse advents occurring during the study procedures are similar to previous studies and to determine if any protocol amendments are needed to address the clarity of study procedures and/or participant education. We will also have an interim review after one year of recruitment at the request of the NIAID DSMB.

9.4 Deviations from Statistical Plan

The principal features of the study design and of the plan for statistical analysis of the data are outlined in this protocol. Any changes in these principal features will require a protocol amendment and will be described in the final report. Any such changes will be subject to review by the IRB, ISM, NIAID, and the FDA.

10 IDENTIFICATION AND ACCESS TO SOURCE DATA

10.1 Identifying Source Data

The investigator will keep accurate records to ensure that the conduct of the study is fully documented. Data derived from source documents will be transferred to protocol-specific CRFs. The results of all clinical and clinical laboratory evaluations will be maintained in the participant's medical records or hospital database and the data will be transferred to clinical CRFs, as applicable.

10.2 Updating Source Documentation

Documents describing the safety profile of an investigational product(s) / Intervention material(s), such as the investigator's brochure and the package insert, will be amended as needed by the investigational product(s) / Intervention material(s) manufacturer to ensure that the description of safety information adequately reflects any new clinical findings.

(The Principal Investigator will provide the Independent Safety Monitor, the NIAID Medical Officer, and the IRB with the most up-to-date versions of the above documents as soon as the Principal Investigator becomes aware of any changes. For purchased investigational product(s) / Intervention material(s), the Principal Investigator will confirm that there are no changes to the package insert every 3 months. In case of package insert changes, the Principal Investigator will notify the Independent Safety Monitor the NIAID Medical Officer, and the IRB.

10.3 Permitting Access to Source Data

The investigational site participating in this study will maintain the highest degree of confidentiality for the clinical and research information obtained from the participants in this clinical trial. Medical and research records will be maintained at each site in the strictest confidence. However, as a part of the quality assurance and legal responsibilities of an investigation, the investigational site will permit authorized representatives of the IND sponsor, NIAID and health authorities to examine (and when required by applicable law, to copy) clinical records for the purpose of quality assurance reviews, audits, and evaluations of the study safety and progress. Unless required by the laws that permit copying of records, only the coded identity associated with documents or with other participant data may be copied (and all personally identifying information will be removed). Authorized representatives as noted above are bound to maintain the strict confidentiality of medical and research information that is linked to identify individuals.

11 QUALITY CONTROL AND QUALITY ASSURANCE

The Principal Investigator will keep accurate records to ensure that the conduct of the study is fully documented. The investigator will ensure that all CRFs and participant study files are legible and complete for every participant.

The Principal Investigator, through the use of a Clinical Research Associate (CRA) will be responsible for the regular review of the conduct of the trial, for verifying adherence to the protocol, and for confirming the completeness, consistency, and accuracy of all documented data and accuracy of source documentation verification. The reports of the CRA will be submitted to the Principal Investigator and the NIAID Project Manager. NIAID will independently review these reports.

When the CRFs are complete, they will be reviewed and signed by the Principal Investigator. All discrepancies identified by the CRA or NIAID will be reviewed, and any resulting queries will be resolved with the Principal Investigator and the CRFs will be amended as needed.

12 ETHICAL CONSIDERATIONS AND COMPLIANCE WITH GOOD CLINICAL PRACTICE

12.1 Statement of Compliance

This study was designed to ensure the protection of participants according to the ethical principles of the Declaration of Helsinki and amendments concerning medical research in human participants. This clinical study will be conducted using current good clinical practice (cGCP), as delineated in Guidance for Industry: E6 Good Clinical Practice Consolidated Guidance 1, and according to the criteria specified in this study protocol. Before study initiation, the protocol and the informed consent documents will be reviewed and approved by NIAID, ISM, IRB, as well as any other appropriate health authorities. Any amendments to the protocol or to the consent materials will also be approved by the appropriate bodies listed above prior to implementation.

12.2 Informed Consent and Assent

The informed consent form will provide information about the study to a prospective participant or participant's legal representative to allow for an informed decision about participation in the study. An age-appropriate assent

form will be provided for children under 14 years of age. Prospective participant or participant's legal representative must be given ample opportunity to review the informed consent and inquire about the results of the study. All participants (or their legally acceptable representative) must read, sign, and date a consent form prior to study participation. Subjects under 14 years old must read, sign, and date an assent form. Consent materials for participants who do not speak or read English will be translated into the participants' appropriate language.

The informed consent form will be revised and receive IRB approval whenever important new safety information is available, whenever the protocol is amended, and/or whenever any new information becomes available that may affect participation in the trial.

A copy of the appropriate informed consent or assent form will be given to a prospective participant for review. The Principal Investigator or an approved designee, will discuss the consent with the prospective participant and answer questions. The prospective participant will be told that being in the trial is voluntary and that he or she may withdraw from the study at any time, for any reason.

